## PROTOCOL APPENDIX B: CYP3A4 INTERACTION TABLE

### CYP3A4 INTERACTION TABLE

(Ascorbate may decrease the plasma/blood concentrations of substrates)

Drugs with ~~strikeout~~ text are antiretroviral drugs that are not allowed for use on this study.

\* 3A4 substrate & inhibitor; # 3A4 substrate & inducer

abiraterone	acetaminophen	ado-trastuzumab	alfentanil
alfuzosin	aliskiren	alitretinoin	almotriptan
alprazolam	ambrisentan	amiodarone*	amitriptyline
amlodipine	amprenavir	apixaban	aprepitant*
aripiprazole	armodafinil#	artemether	asenapine
astemizole	atazanavir*	atorvastatin	avanafil
axitinib	beclomethasone	bedaquiline	benzphetamine
bexarotene	bisoprolol	boceprevir	bortezomib
bosentan#	bosutinib	brentuximab	bromazepam
bromocriptine	budesonide	buprenorphine	buspirone
busulfan	cabazitaxel	cabozantinib	caffeine
canagliflozin	carbamazepine#	cevimeline	chlor diazepoxide
chloroquine	chlorpheniramine	ciclesonide	cilostazol
cinacalcet	cisapride	citalopram	clarithromycin*
clindamycin	clobazam	clomipramine	clonazepam
clopidogrel	clorazepate	clozapine	cobicistat*
cocaine	codeine	colchicine	conivaptan*
crizotinib	cyclobenzaprine	cyclophosphamide	cyclosporine*
dantrolene	dapsone	darifenacin	<del>darunavir</del>
dasatinib	delavirdine*	desogestrel	dantrolene
dexamethasone#	dexlansoprazole	dextromethorphan	diazepam
diclofenac	dienogest	dihydroergotamine	diltiazem*
disopyramide	docetaxel	dofetilide	dolasetron
domperidone	donepezil	doxorubicin	dronedarone
droperidol	dutasteride	efavirenz*#	eletriptan
elvitegravir	enzalutamide	eplerenone	ergoloids
ergonovine	ergotamine	erlotinib	erythromycin*
escitalopram	esomeprazole	estazolam	estradiol
estradiol valerate	estrogens	eszopiclone	ethinyl estradiol
ethosuximide	etonogestrel	etoposide	etravirine
everolimus	exemestane	felbamate	felodipine
fentanyl	fesoterodine	fexofenadine	finasteride
fingolimod	flunisolide	flurazepam	flutamide
fluticasone	<del>fosamprenavir</del> *	fosaprepitant	fulvestrant
galantamine	gefitinib	gransetron	guanfacine
haloperidol*	hydrocodone	hydrocortisone	ifosfamide
iloperidone	imatinib*	imipramine	indacaterol
<del>indinavir</del> *	irinotecan	isosorbide dinitrate	isosorbide mononitrate

### CYP3A4 INTERACTION TABLE

(Ascorbate may decrease the plasma/blood concentrations of substrates)

Drugs with ~~strikeout~~ text are antiretroviral drugs that are not allowed for use on this study.

\* 3A4 substrate & inhibitor; # 3A4 substrate & inducer

isradipine	itraconazole*	ivacaftor	ixabepilone
ketamine	ketoconazole*	lansoprazole	lapatinib
lercanidipine	letrozole	levonorgestrel	lidocaine*
linagliptin	lomitapide	loperamide	<del>lopinavir</del>
loratadine	losartan	lovastatin	lumefantrine
lurasidone	<del>maraviroc</del>	marijuana	medroxyprogesterone
mefloquine	meloxicam	mestranol	methadone
methylergonovine	methylprednisolone	miconazole*	midazolam
mifepristone	mirabegron	mirtazapine	modafinil
mometasone	montelukast	nateglinide	nefazodone*
<del>nelfinavir*</del>	<del>nevirapine#</del>	nicardipine*	nifedipine
nilotinib	nimodipine	nisoldipine	nitrendipine
norethindrone	norgestrel	nortriptyline	omeprazole
ondansetron	ospemifene	oxybutynin	oxycodone
paclitaxel	paliperidone	palonosetron	pantoprazole
paricalcitol	paroxetine	pazopanib	perampanel
perphenazine	pimozide	pioglitazone	pomalidomide
ponatinib	prasugrel	prednisolone	prednisone
primaquine	progesterone/ progestins	propafenone	propranolol
quazepam	quetiapine	quinidine*	quinine
rabeprazole	ramelteon	ranolazine	regorafenib
repaglinide	rifabutin#	<del>rilpivirine</del>	risperidone
<del>ritonavir*</del>	rivaroxaban	roflumilast	romidepsin
ruxolitinib	salmeterol	<del>saquinavir*</del>	saxagliptin
selegiline	sertraline	sibutramine	sildenafil
silodosin	simvastatin	sirolimus	sitagliptin
solifenacin	sorafenib	sufentanil	sunitinib
tacrolimus	tadalafil	tamoxifen	tamsulosin
<del>telaprevir</del>	telithromycin*	temsirolimus	teniposide
terfenadine	testosterone	tetracycline*	theophylline
tiagabine	ticagrelor	ticlopidine	tinidazole
<del>tipranavir</del>	tofacitinib	tolterodine	tolvaptan
topotecan	toremifene	tramadol	trazodone
triazolam	trimethoprim	trimetrexate	trimipramine
ulipristal	vandetanib	vardenafil	vemurafenib
venlafaxine	verapamil*	vilazodone	vinblastine
vincristine	vinorelbine	vismodegib	voriconazole
warfarin	zaleplon	zileuton	ziprasidone
zolpidem	zonisamide	zopiclone	

References:

1. Lexi-comp On-line. Cytochrome P450 Enzymes: Substrates, Inhibitors, and Inducers. (accessed 1/16/15)
2. Pharmacist's Letter/Prescriber's Letter. Cytochrome P450 Drug Interactions. October 2013.

## APPENDIX D: DATA AND SAFETY MONITORING PLAN

### Type of Clinical Trial:

 Investigator-initiated (UI/HCCC)	 Investigator-initiated, participating site
 Pilot study	 Phase I
 Phase I/II	 Phase II
 Phase III	 Compassionate-use/Expanded Access
 Interventional Treatment	 Interventional Non-Treatment
 Non-Interventional	

### Study risk-level:

 Level 1—low risk of morbidity or death, * <1% of death or any adverse event
 Level 2—risk of death* <1% or any adverse event 1% – 5%
 Level 3—risk of death* 1% – 5% or grade 4 – 5 SAE 1% – 5%
 Level 4—risk of death* >5% or grade 4 – 5 SAE >5%
 Drugs being used on a “compassionate” basis

\* *Risk of death* refers specifically to 100-day treatment-related mortality

---

### Reporting and Monitoring Requirements:

All institutional investigator initiated trials (IITs), regardless of assigned risk level are subject to routine DSMC monitoring activities which may include but are not limited to review of signed consent documents, eligibility and adverse event reporting.

All institutional IITs have the following **reporting requirements** as part of their DSMP:

- Register all subjects in HCCC’s Clinical Trial Management System, OnCore
- Document Adverse Events
- Document protocol deviations
- Provide an annual progress report to the DSMC via OnCore data export

### Selected monitoring strategy based on risk-level:

#### **Risk Level 4**

Interventional treatment trials involving investigational agents or devices with a risk of death\* (>5% or grade 4 – 5 SAE >5%), e.g. all investigator initiated INDs, most Phase I/II trials, gene therapy, gene manipulation or viral vector systems high-risk clinical procedures if performed solely for research purposes. The use of a new chemical or drug for which there is limited or no available safety data in humans.

### Study Safety Review

An independent study monitor and/or the DSMC Chair (or designee), will review study data (provided by the PI/available in OnCore) and communicate with the PI at least biannually. A copy of this communication will be forwarded to the DSMC and PRMC Chairs.

### Additional Reporting Requirements:

- A scanned copy of the completed eligibility checklist, with screening information and PI signature, will be attached in OnCore for ongoing review by DSMC staff.
- Serious adverse events will be entered directly into an OnCore SAE report by the research team. OnCore will send an automatic notification to the DSMC Chair/acting Chair and staff for review.
- The DSMC utilizes a risk-based monitoring approach. The trial's research records will be monitored at minimum twice per year. Monitoring may be done more frequently depending on the protocol, risks to subjects, reported serious/adverse events, patient population and accrual rate. Records for a minimum of 25% of subjects will be monitored for the entire study.

Monitoring will involve the following:

- review eligibility of patients accrued to the study,
- check for the presence of a signed informed consent,
- determine compliance with protocol's study plan,
- determine whether SAEs are being appropriately reported to internal and external regulatory agencies,
- compare accuracy of data in the research record with the primary source documents,
- review investigational drug processing and documentation,
- assess cumulative AE/SAE reports for trends and compare to study stopping rules.

### **Routine Adverse Event Reporting**

For non-serious Adverse Events, documentation must begin from the time the subject signs the informed consent document and continue through the 30-day follow-up period after the last dose of study drug.

Collected information should be recorded in the electronic/Case Report Forms (eCRF/CRF) for that subject. A description of the event, its severity or toxicity grade (according to [NCI's Common Toxicity Criteria \(CTCAE\)](#)), onset and resolved dates (if applicable), and the relationship to the study drug should be included. Documentation should occur in real time. The principal investigator has final responsibility for determining the attribution of the event as it is related to the study drug.

### **Serious Adverse Event Reporting**

For any experience or condition that meets the definition of a serious adverse event (SAE), recording of the event must begin after signing of the informed consent and continue through the 30 day follow-up period after treatment is discontinued.

Investigators must report to the DSMC any serious adverse events (SAE), whether or not they are considered related to the investigational agent(s)/intervention (21 CFR 312.64). SAEs must be reported via an OnCore SAE Report within 24 hours of learning of the event.

An adverse event is considered **serious** if it results in ANY of the following outcomes:

1. Death
2. A life-threatening adverse event
3. An adverse event that results in inpatient hospitalization OR prolongation of existing hospitalization for  $\geq$  24 hours
4. A persistent or significant incapacity or substantial disruption of the ability to conduct normal life functions
5. A congenital anomaly/birth defect.
6. Important Medical Events (IME) that may not result in death, be life threatening, or require hospitalization may be considered serious when, based upon medical judgment, they may jeopardize the patient or subject and may require medical or surgical intervention to prevent one of the outcomes listed in this definition. (FDA, [21 CFR 312.32](#); [ICH E2A](#) and [ICH E6](#)).

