## 7.3 FDA reporting requirements [[name], sponsor]

Adverse events meeting the criteria of *serious*, *unexpected*, and *attributed* (possible, probable, or definite) to ascorbate must be reported by the sponsor or the sponsor's appointed designee to the FDA:

- Serious adverse events *only* [21 CFR 312.32]
- Attributable to ascorbate with a causal relationship (possible, probable, or definite)
- Unexpected, as defined by the FDA: "...not listed in the investigator brochure or is not listed at the specificity or severity that has been observed; or, if an investigator or, if an investigator brochure is not required or available, is not consistent with the risk information described in the general investigational plan or elsewhere in the current application, as amended."

To help the sponsor meet these reporting requirements, all serious adverse events that are unexpected and attributed to study drug must be reported to the sponsor within 1 business day. This coincides with SAE reporting requirements for the DSMC.

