## 7.5 Serious Adverse Event Reporting to DSMC

For any experience or condition meeting the definition of a serious adverse event (SAE; 21CFR312.32), from the first day of study treatment and typically continue through the 30 day follow-up period after treatment is discontinued.

Investigators must report to the DSMC any SAE, regardless of attribution to study drug. SAEs must be reported *via* an OnCore SAE Report within 1 business day of learning of the event.

An adverse event is considered **serious** if it results in ANY of the following outcomes:

- Death
- A life-threatening adverse event
- An adverse event that results in inpatient hospitalization OR prolongation of existing hospitalization for  $\geq 24$  hours
- A persistent or significant incapacity or substantial disruption of the ability to conduct normal life functions
- A congenital anomaly/birth defect.
- Important Medical Events (IME) that may not result in death, be life threatening, or require hospitalization may be considered serious when, based upon medical judgment, they may jeopardize the patient or subject and may require medical or surgical intervention to prevent one of the outcomes listed in this definition. ([21 CFR 312.32](#); [ICH E2A](#) and [ICH E6](#)).

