# **11. MEASUREMENT OF EFFECT**

## **11.1 Pathologic Response**

4 to 6 weeks after the end of neoadjuvant therapy, patients will undergo resection of the treated tumor. The SOC pretreatment biopsy and all the resected tumor samples will be reviewed by the same pathologist.

The percentage of post treatment tumor necrosis must be documented. The primary end point for this study is pathologic complete response (pCR), and is defined as  $\geq 95\%$  tumor necrosis following concurrent radiation therapy and ascorbate

Treatment effect on the resected overlying skin tissue will be graded and recorded (to be done by the pathologist). This will be compared with historical controls.

Additional immunohistochemical studies will be performed as determined by the pathologist.

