**Response Measurement Criteria:**

Measurements of the tumor in its largest dimension should be obtained at baseline and at the end of the treatment phase, prior to surgical resection.

Response criteria should be by RECIST v 1.1.

- Complete response is the disappearance of all target lesions.
- Partial response is a 30% decrease in the sum of the longest dimensions of the target lesions, relative to baseline.
- Progressive disease is an increase of 20% or more in the sum of the longest dimension of target lesions
- Stable disease is a decrease in the tumor size of < 30% or an increase of < 20%.
- Antitumor response by pathologic assessment will be performed on the resected tumors. Pathologic assessment will be performed per institutional guidelines.
- The percent of tumor necrosis and the percent of tumor-infiltrating lymphocytes will be documented.
- Complete pathological response will be considered  $\geq 95\%$  pathologic tumor necrosis.

Radiologic response will be evaluated in this study using the new international criteria proposed by the revised Response Evaluation Criteria in Solid Tumors (RECIST) guideline (version 1.1) [*Eur J Ca* 45:228-247, 2009]. Changes in the largest diameter (unidimensional measurement) of the tumor lesions and the shortest diameter in the case of malignant lymph nodes are used in the RECIST criteria.

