### **Study Stopping and Pausing Rules**

The study will pause enrollment and stop treatment for all participants if any of the following events occur pending submission to Regulatory Agencies and review by the DSMC and IRB who will determine if the study may resume:

- Any event of treatment related death in a study subject

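### Required all-cause recording of serious and routine adverse events ends at day 30, about when the mandated resection takes place (days 28 to 42), and nothing clearly requires recording or prompt all-cause reporting of SAEs after that

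*Combined protocol and SAP*

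**What the plan says.** **Recording windows.** For SAEs, Appendix D (Serious Adverse Event Reporting) states that "recording of the event must begin after signing of the informed consent and continue through the 30 day follow-up period after treatment is discontinued". Section 7.5 gives the same end but says that it will "typically continue through the 30 day follow-up period after treatment is discontinued". For non-serious events, Appendix D (Routine Adverse Event Reporting) has documentation "continue through the 30-day follow-up period after the last dose of study drug". Both SAE sections require every SAE to go to the DSMC whatever its cause: within one business day in Section 7.5, within 24 hours in Appendix D.

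**Surgery.** Section 11.1 says: "4 to 6 weeks after the end of neoadjuvant therapy, patients will undergo resection of the treated tumor". Sections 5.1, 5.2 and 5.7 give the same 4 to 6 weeks from the end of radiation. Section 5.2 continues ascorbate to the end of radiation. Section 11.3 places the final tumor measurement "at the end of the treatment phase, prior to surgical resection", so the treatment phase ends before the operation.

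**Uses of post-operative data.** The pause rule in Appendix D is triggered by "Any event of treatment related death in a study subject". Section 12.2 plans to set wound-complication rates, with exact 95% confidence intervals, against historical controls. It names no period over which wound events are collected.

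**The concern.** Resection is a protocol step and supplies the specimen for the primary endpoint. Section 5.7.11 anticipates wound complications in about one third of patients. Complications of the operation can only arise after it, yet both recording windows close before it or within two days of it.

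Two things are at stake. The first is oversight. The plan sends all SAEs to the DSMC regardless of cause, so that the committee does not depend on the investigator's attribution. If sites treat day 30 as the end of the duty, a post-operative death or serious wound event judged unrelated has no clear prompt route to the committee. The second is the wound comparison in Section 12.2. Wound events missed because the window had closed would lower the observed rate and make the combination look better than it is against historical controls.

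**Working it through.** The plan gives no figure of its own on this point. The check is a count of calendar days followed by a comparison of the reporting routes.

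**Day count.** Let day 0 be the last radiation fraction and, first, also the last ascorbate dose. Assume no post-operative boost.

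- Permitted surgery days: 4 to 6 weeks = days 28 to 42, so 42 − 28 + 1 = 15.
- Both windows close at day 30. Surgery days after that: 31 to 42, so 42 − 31 + 1 = 12 of 15.
- Post-operative days inside the window: surgery on day 28 gives 30 − 28 = 2; day 29 gives 1; day 30 or later gives 0.

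**Earlier last dose.** If the clock runs from an ascorbate dose given g days before the last fraction, the window closes at day 30 − g. The number of surgery days outside becomes 13 for g = 1, 14 for g = 2 and 15 for g of 3 or more. A gap of 5 days arises if the 15 doses in Section 5.3 are given Monday, Wednesday and Friday over 5 weeks alongside 28 fractions: counting the first treatment day as 0, the last dose is on day 32 and the last fraction on day 37. So 12 is the lowest count without a boost.

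**The week 4 to 6 visit.** The Section 10.1 calendar ticks adverse events at the visit 28 to 42 days after the last dose. That visit can precede surgery or follow it by at most 42 − 28 = 14 days. Of the first 30 post-operative days, between 30 − 14 = 16 and 30 remain uncovered even if the visit is counted. The calendar's follow-up column has no adverse-event tick.

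**Other routes after day 30.**

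- *Section 7.2 (IRB):* no end date, but the event must be attributed to ascorbate.
- *Section 7.3 (sponsor and FDA):* "all serious adverse events that are unexpected and attributed to study drug must be reported to the sponsor within 1 business day". It adds: "This coincides with SAE reporting requirements for the DSMC". There is no end date, but the event must already be judged both unexpected and related. Wound complications are anticipated, so many may not qualify as unexpected.
- *Pause rule:* no end date, but the death must be judged treatment-related.
- *Section 10.1, footnote c:* at least monthly follow-up until resolution, for ascorbate-related events only.
- *Appendix D review:* an independent monitor or the DSMC Chair at least biannually, and record monitoring at least twice a year on at least 25% of subjects.
- *Survival follow-up (Sections 5.10 and 10.1):* about every 12 weeks, possibly by passive chart review. It captures deaths from any cause, but not promptly as SAEs.
- *Post-operative boost (Sections 5.7.9 and 5.7.10):* might restart the SAE clock. It is discretionary, and Section 5.7.5 discourages an external-beam boost. The routine window is tied to study drug, so on its wording a boost would not extend it.

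Each route either needs attribution first or is slow or partial. None clearly requires all-cause recording past surgery.

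**The case against.** The strongest reply is textual. Only the recording sentences carry the 30-day limit. The sentences on reporting to the DSMC have no end date, and their clock runs from learning of the event. Section 7.5 also hedges its window. A reader might infer that the duty to report to the DSMC itself stops at day 30, but the documents do not say so. What survives is that the reporting sentences sit directly beneath a recording period that ends at day 30, and nothing plainly requires a later event to be recorded. Sites could reasonably read it either way.

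Four other inferences go further than the text allows.

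- *The committee would never see a late death.* Survival follow-up, the biannual review, source-data checks and the DSMC's standing access to subject data in OnCore all remain. What is lost is speed and completeness.
- *Twelve of 15 means 80% of patients.* The count is of permitted dates. The documents give no distribution of surgery dates.
- *The window disables the pause rule.* That rule depends on attribution on every study day and has no time limit. A longer window would not change who judges causality; it would only let the DSMC see more cases promptly.
- *The wound comparison will falsely favor ascorbate.* Take the 35% in Section 1.4 as an assumed control rate, since Section 12.2 names none. About 9 of 25 patients would be affected (25 × 0.35 = 8.75). Recording only 3 gives 12% (exact 95% CI 2.5 to 31.2%), which excludes 35%; recording 4 gives 4.5 to 36.1%, which does not. A false exclusion therefore needs 6 of 9 events lost. Across the 25 to 44% range in Section 1.4 it needs 5 of 6 lost at the low end and 6 of 11 at the high end, that is 55 to 83% of events. Nothing supports losses of that size. Nothing says that the wound rate comes only from the adverse-event log either: Appendix D has the investigator and statistician approve the case report forms, and patients at this single institution stay under clinical follow-up.

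Wound complications are also absent from the objectives in Section 3, and no decision rule rests on them.

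**Conclusion.** The gap is real but bounded. As written, required all-cause recording ends at day 30, while the mandated resection falls on days 28 to 42. At least 12 of the 15 permitted surgery days are beyond the limit, and at most 2 post-operative days are covered. This assumes that treatment is discontinued on the last day of radiation, as Section 11.3 implies, and that no boost is given; an earlier last dose makes the count worse.

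The consequence is less prompt and less complete information on post-operative SAEs. If the Section 12.2 wound rate is drawn from adverse-event records, it would tend to be biased downward, by an amount that cannot be estimated from the documents. The tumor-necrosis endpoint and its threshold of 6 responders in 25 are unaffected. This is a worthwhile, inexpensive improvement, not a flaw that undermines the trial.

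**What to change.** Amend Section 7.5 and both adverse-event windows in Appendix D as follows:

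1. Recording and all-cause reporting run through 30 days after resection or 30 days after the last study treatment, including any post-operative boost, whichever is later. If there is no resection, they run through 30 days after the last study treatment.
2. The planned surgical admission and its expected length of stay are not SAEs. Without the second part, every stay prolonged by 24 hours or more could be argued to be reportable.
3. Wound complications for Section 12.2 are collected over this same window.

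**Cost.** The window would close between day 58 (28 + 30) and day 72 (42 + 30) after radiation instead of day 30. That is 28 to 42 more recording days per unboosted patient, or 700 to 1,050 patient-days over 25 patients. At the one-third rate in Section 5.7.11, about 8 patients (25 ÷ 3 = 8.3) would have a wound complication of any grade to record; those meeting a seriousness criterion would also need an SAE report. Some additional reports of routine surgical complications are the main downside. The change uses the existing OnCore forms, staff and committee.
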